6. STATISTICAL METHODOLOGY

[figure not shown]
[figure not shown]
6.1. Study Subjects

The number of subjects who complete the screening phase 
 and the number of subjects who discontinue the screening phase 
 together with the primary reason for discontinuation will be summarized overall on the screened population. The number of randomized subjects included will also be displayed.

Subject disposition will be provided on the randomized population by treatment sequence and overall summarizing the number of subjects randomized and the number of treated subjects. The number of subjects who complete the treatment 
 and the number of subjects who discontinue the treatment 
 together with the reason for study discontinuation will be provided. Similarly, the number of subjects who complete the study 
 and the number of subjects who

[figure not shown]
| | |
|---|--|
|  | Statistical Analysis Plan |
| | Sponsor: Alfasigma S.p.A. Protocol: VE-CIP2001/2021 |

discontinue the study 
 together with the reason for study discontinuation will be provided.

In addition, the number of subjects who enter in each period including wash-out/follow-up (i.e., performed the corresponding SOT visit) and the number of subjects who complete the treatment, who perform switch in treatment period, who discontinue the treatment together with the reason for treatment discontinuation, who complete wash-out/follow-up, who perform switch in the wash-out period or who discontinue the wash-out/follow-up will be also provided considering each period. 

The numerosness of the analysis populations (SS, FAS, mFAS1,  and PPS) will be described and the reasons for excluding a subject from an analysis population will be provided on the randomized population by treatment sequence.

The number of subjects reporting at least one major protocol deviation and the number of subjects reporting each considered major PD will be summarized on the randomized

| | |
|---|--|
|  | Statistical Analysis Plan |
| | Sponsor: Alfasigma S.p.A. Protocol: VE-CIP2001/2021 |

population by treatment sequence and overall. Similarly, the number of subjects reporting at least one minor protocol deviation and the number of subjects reporting each considered minor PD will be summarized on the randomized population by treatment sequence. The list of confirmed protocol deviations and their classification as major/minor was defined in the specific protocol deviation handling plan.

[figure not shown]

Table 6.1-1: 

6.2. Background and Demographic Characteristics

Background and demographic characteristics will be summarized descriptively by treatment sequence and overall on the FAS, mFAS1.

[figure not shown]
| | |
|---|--|
|  | Statistical Analysis Plan |
| | Sponsor: Alfasigma S.p.A. Protocol: VE-CIP2001/2021 |

- 

Medical and surgical history findings will be summarized by System Organ Class and Preferred Term according to the MedDRA dictionary, 

 Subjects will only be counted once per MedDRA level, and the medical history will be sorted by descending incidence of SOCs and then PTs in the overall group. Medical and surgical history findings will be summarized separately:

- 
- 
- 
- 
- 

[figure not shown]
[figure not shown]
Prior medication (except ) administered during the last 30 days before screening visit will be summarized 

Prior  administered before screening visit will be summarized 

In addition, the following variables will be summarized at Visit 1 on the FAS population according to treatment sequence:

- 
- 

| | |
|---|--|
|  | Statistical Analysis Plan |
| | Sponsor: Alfasigma S.p.A. Protocol: VE-CIP2001/2021 |

- 

6.3. Efficacy Evaluation

6.3.1. Primary efficacy analysis

Definition of primary endpoint

The primary endpoint is the change in weekly global gastrointestinal symptoms average index score from pre-treatment (Baseline/Reference, depending on the period) to the end of each treatment period.

The weekly global gastrointestinal symptoms average index score is obtained by averaging the scores for each of the 4 symptoms assessed weekly: abdominal pain, bloating, nausea and vomiting.

Each symptom (i.e., abdominal pain, bloating, nausea, vomiting) was rated using a recall period of 7 days and a Likert scale with the following categories:

- 0 – Absent
- 1 - Mild (not influencing usual activities)
- 2 - Moderate (diverting from, but not urging modification of, usual activities)
- 3 - Severe (influencing usual activities markedly enough to urge modifications)
- 4 - Extremely severe (precluding daily activities)

[figure not shown]
[figure not shown]
[figure not shown]

Analysis methodology

| | |
|---|--|
|  | Statistical Analysis Plan |
| | Sponsor: Alfasigma S.p.A. Protocol: VE-CIP2001/2021 |

Considering the evaluable pairs  the  will be summarized 

Of note, each subject should be evaluated twice: once for each cycle. Consequently, each subject can contribute to 0, 1 or 2 pairs and only data that constitute pair evaluable for primary endpoint will be considered in this and in the following analysis.

Differences between velusetrag and placebo will be computed within each cycle 

These analyses will be provided on the mFAS1 without any missing data imputation as primary analysis.

Finally, a listing will be provided on Randomized population considering the intake of each  collected in the eDiary together with the individual gastrointestinal symptoms and the weekly global gastrointestinal symptoms average index score.

Data handling rules

Missing data will be handled as described in [Section 4.4.2](#).

[figure not shown]
Sensitivity analysis

| | |
|---|--|
|  | Statistical Analysis Plan |
| | Sponsor: Alfasigma S.p.A. Protocol: VE-CIP2001/2021 |

6.3.2. Secondary efficacy analysis

| | |
|---|--|
|  | Statistical Analysis Plan |
| | Sponsor: Alfasigma S.p.A. Protocol: VE-CIP2001/2021 |

These analyses will be performed only on mFAS1 and  without missing imputation.

Definition

The  will be computed as described in section 6.3.1.

The proportion of subjects with change between the end of treatment and pre-treatment value ≤ -1 point will be computed and considered as “Success” while the proportion of subjects with change between the end of treatment and pre-treatment value > -1 will be considered as “Failure”.

Data handling rules

No missing imputation will be performed.

Definition

Each symptom (i.e., ) was rated using a recall period of 7 days and a Likert scale with the following categories:

0 – Absent

1 - Mild (not influencing usual activities)

| | |
|---|--|
|  | Statistical Analysis Plan |
| | Sponsor: Alfasigma S.p.A. Protocol: VE-CIP2001/2021 |

- 2 - Moderate (diverting from, but not urging modification of usual activities)
- 3 - Severe (influencing usual activities markedly enough to urge modifications)
- 4 - Extremely severe (precluding daily activities)

The endpoint is the [redacted] score from pre-treatment to the end of each treatment period. A [redacted] represents improvement.

[redacted]

[redacted]

[redacted]

Definition

The number of [redacted] and [redacted] will be provided in the eDiary every 7 days together with the evaluation of the [redacted] of [redacted] on average according to [redacted] scale.

Changes in the number of [redacted] and number of [redacted] will be computed between the end of each treatment period and the pre-treatment (Baseline/Reference).

[redacted]

[redacted]

[redacted]

[redacted]

| | |
|---|--|
|  | Statistical Analysis Plan |
| | Sponsor: Alfasigma S.p.A. Protocol: VE-CIP2001/2021 |

[figure not shown]
[figure not shown]
[figure not shown]
[figure not shown]

Data handling rules

[figure not shown]
[figure not shown]
[figure not shown]
No missing imputation will be performed.

Definition

The  on average was recorded according to  by means of eDiary. The  scale ranges from 1, which corresponds to Type 1 (i.e., separate hard lumps, like nuts that indicates ) to 7, which corresponds to Type 7 (i.e., watery, no solid piece that indicates ).

The  scale will be categorized according to the following categories that indicates the subjects' status:

- 
- 
- 

[figure not shown]
Data handling rules

[figure not shown]
No missing imputation will be performed.

| | |
|---|--|
|  | Statistical Analysis Plan |
| | Sponsor: Alfasigma S.p.A. Protocol: VE-CIP2001/2021 |

Definition

The  will be provided in the eDiary every 7 days according to a scale from 0=very unhappy to 10=very happy.

[figure not shown]
[figure not shown]
[figure not shown]
Changes in  will be computed between the end of treatment number and the pre-treatment number (Baseline/Reference). A positive change represents an improvement.

[figure not shown]

[figure not shown]
Definition

The  will be computed based on the   to assess  consists in timed and standardized measurement of  after the ingestion of a solution of water and .

This evaluation will be performed only during the first treatment period of the study.

Changes in  will be computed between the post-treatment  (i.e., end of first treatment period at Visit 3 (EOT-1)) and the pre-treatment  (i.e., Screening value at Visit 1).

Data handling rules

No missing imputation will be performed.

[figure not shown]
[figure not shown]

[figure not shown]

| | |
|---|--|
|  | Statistical Analysis Plan |
| | Sponsor: Alfasigma S.p.A. Protocol: VE-CIP2001/2021 |

[figure not shown]

Definition

 levels are , ,  and . Their levels will be collected at pre-treatment (Baseline/Reference) and at the end of follow-up after the fourth period and at ETV and ESV.

Changes in  will be computed between the end of each 2-week wash-out period (or follow up period) and the relevant pre-treatment values (Baseline/Reference)(i.e., for period 1: levels at V4 – levels at V1; for period 2: levels at V6 – levels at V4; for period 3: levels at V8 – levels at V6 and for period 4: levels at V10 – levels at V8).

[figure not shown]
Data handling rules

No missing imputation will be performed.

| | |
|---|--|
|  | Statistical Analysis Plan |
| | Sponsor: Alfasigma S.p.A. Protocol: VE-CIP2001/2021 |

Definition

For each , the subject provides daily the status of the intakes:

- Not taken
- Taken at the prescribed dose
- Taken at reduced dose
- Taken at increased dose

For each  collected in the eDiary, excluding antacids 

 the following flag are calculated:

- Increase flag: for each day, a drug will be considered as taken at increase dose

Baseline/Reference is defined as the last information collected in the eDiary in the previous phase. It will be Day -1 for Treatment Period 1, the last day in Treatment Period 1 for Wash-out Period 1 and so on.

These flags will be reviewed and updated by means of Medical Review to evaluate if the computed flags are clinically consistent.

[figure not shown]
[figure not shown]
[figure not shown]
- 
- 

[figure not shown]
| | |
|---|--|
|  | Statistical Analysis Plan |
| | Sponsor: Alfasigma S.p.A. Protocol: VE-CIP2001/2021 |

[figure not shown]
- 
- 
- 
- 
- 
- 
- 
- 
- 
- 

[figure not shown]
The numerator will be considered as follows:

- Proportion of days with dose increased (at least 1 medication): 

- Proportion of days with dose increased (1-2 medications): 

- Proportion of days with dose increased (≥ 3 medications): 

- Proportion of days with dose decreased (at least 1 medication): 

[figure not shown]
- Proportion of days with dose decreased (1-2 medications): 

- Proportion of days with dose decreased (≥ 3 medications): 

- Proportion of days with drug added (at least 1 medication): 

- Proportion of days with drug removed (at least 1 medication): 

Analysis methodology

| | |
|---|--|
|  | Statistical Analysis Plan |
| | Sponsor: Alfasigma S.p.A. Protocol: VE-CIP2001/2021 |

[figure not shown]
[figure not shown]
[figure not shown]
[figure not shown]

Data handling rules

No missing imputation will be performed.

[figure not shown]
Definition

The  is a  used to assess generic  outcomes from the subject's perspective. It is often used as a  measure. Generic subject-reported outcome (PRO) measures like the  including the impact of any and all illnesses on a broad range of functional domains. The  consists of a subset of  from the  covering the same  domains of , including 

 (norm based score) that represents  and  components of  and  will be derived by means of the 

Analysis methodology

Data handling rules

No missing imputation will be performed.

6.3.2.11. 

Definition

The number of  during each treatment period will be collected and analyzed as well as the number of  during each wash-out/follow-up period.

| | |
|--|---|
| | Statistical Analysis Plan |
| | 
Sponsor: Alfasigma S.p.A.
 
Protocol: VE-CIP2001/2021
 |

Analysis methodology

[Redacted]

[Redacted]

Data handling rules

No missing imputation will be performed.

[Redacted]

[Redacted]

Definition

The [Redacted] is used to provide an evaluation of the type of diet followed by the subject. [Redacted]

[Redacted]:

| | | |
|------------|------------|------------|
| [Redacted] | [Redacted] | [Redacted] |

Analysis methodology

[Redacted]

[Redacted]

| | |
|---|--|
|  | Statistical Analysis Plan |
| | Sponsor: Alfasigma S.p.A. Protocol: VE-CIP2001/2021 |

Data handling rules

No missing imputation will be performed.

Definition

The number of  during each treatment period will be collected and analyzed as well as the number of  during each wash-out/follow-up period.

Analysis methodology

Data handling rules

No missing imputation will be performed.

Definition

[figure not shown]
The effect of  will be evaluated considering the following set of variables previously described:

- 

| | |
|---|--|
|  | Statistical Analysis Plan |
| | Sponsor: Alfasigma S.p.A. Protocol: VE-CIP2001/2021 |

— 

Analysis methodology

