In case, during a treatment period or during a washout period, a subject should experience an exacerbation of the CIPO related gastrointestinal symptoms that is not controlled by permitted medications and is not judged as an adverse event, he/she will attend an early switch visit (ESV) at the clinical site. After being reassessed, he/she will be offered to directly switch to the next scheduled treatment period (SOT-2 or SOT-3 or SOT-4) without completing the ongoing treatment or washout period. Only one early switch is possible during the study. ESV will be Day 1 of the relevant period (SOT-2 or SOT-3) based on the timing of early switch.

In case of ESV/SOT-2 or ESV/SOT-3 or ESV/SOT-4, the subsequent visits will follow the relevant sequential number (see Study Schedule of Assessments).

will be registered on Day-1 (taking into consideration the symptoms relevant to the last 7 days including Day-1) and weekly after randomization, during both treatment and wash out periods, as appropriate according to the Study Schedule of Assessments using a subject's e-diary, until End of Follow-up or in case of ETV or ESV.

[figure not shown]
In addition, investigational product intake and time will be registered by the subjects in the e-diary during the treatment periods daily.

will be also assessed at screening and then, after randomization during the study according to "Study Schedule of Assessments".

At the screening visit and at the end of the first 4-week treatment period, will be performed in order to assess

In order to assess in all subjects on Visit 2 (Day 1) and Visit 3 (Day 28 ± 1), blood samples for assessment of plasma velusetrag and THRX 830449 (metabolite) concentrations will be collected.

Figure 1: Schematic study design

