16.3.2 Secondary Efficacy Endpoints and Statistical Model of Analysis

Continuous efficacy endpoints will be summarized and analyzed in the same way as the primary endpoint. In case of deviation from normality, non-parametric method will be considered. Binary outcome will be compared between treatments with an odds ratio and confidence interval using logistic model and Cochran-Mantel-Haenszel test. Poisson modelling will be used for count data. Full details will be provided in the SAP.

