| Draft Version 1.1 | 20-APR-2023 | 
Section 1.1 is updated to report the decision to not considered the variable stratum in the efficacy analyses and all efficacy sections are updated consequently (i.e., 6.3.1, 6.3.2.1, 6.3.2.2, 6.3.2.4, 6.3.2.8).
 
Section 6.1 is updated to better clarify how subject disposition will be described and to drop tables by stratum.
 
Time from CIPO diagnosis date to informed consent signature described in Section 6.2 is computed in years instead of months.
 
The analysis of primary endpoint on FAS is removed in section 6.3.1.
 
Section 6.3.2.9 related to [REDACTED] is updated including additional details.
 
Section 6.3.2.11 [REDACTED] and section 6.3.2.13 [REDACTED] are updated to consider the variables as
 | Sponsor's review |

| | |
|--|---|
| | Statistical Analysis Plan |
| | 
Sponsor: Alfasigma S.p.A.
 
Protocol: VE-CIP2001/2021
 |

| Status and Version | Release Date | Change Description | Reason/Comment |
|----------------------|--------------|--|------------------|
| | | 
categorical and to include data collected for wash-out/follow-up period and statistical model for [REDACTED]. [REDACTED] are removed.
 
Formal adjustment for section 6.4.3.
 
Further details are included for listings with abnormal values in section 6.4.4 and 6.4.6.
 
[REDACTED] are updated in section 6.4.4.
 | |
| Draft Version 1.2 | 09-MAY-2023 | 
Section 1.1 updated with further details on binary outcome and count data. Fisher exact test was included in the section 6.3.2.2 and 6.3.2.13.
 
ATC codes to identify opioids treatments in section 3.3.3 were updated as well as the ATC code to identify patients who took antibiotics in section 6.3.2.7.
 
Including also start date for prior medications (including the [REDACTED] [REDACTED] start date of medical history condition on which imputation rules for partial dates will be applied to compute the study day.
 
Management of [REDACTED] collected with different unit of measurements where there isn't conversion factor applicable to uniform the unit are described for [REDACTED].
 
Similarly, management of [REDACTED] collected as greater than (>) or lower than (<) will be also described.
 
Mixed models for efficacy parameters considered as continuous variables were updated considering the reference of
 | Sponsor's review |

| | |
|--|---|
| | Statistical Analysis Plan |

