For efficacy evaluation after the discontinuation of each treatment, the reference for changes computation is defined as the end of treatment visit for each period: Visit 3 (EOT-1) for period 1, Visit 5 (EOT-2) for period 2, Visit 7 (EOT-3) for period 3 and Visit 9 (EOT-4) for period 4.

| | |
|---|--|
|  | Statistical Analysis Plan |
| | Sponsor: Alfasigma S.p.A. Protocol: VE-CIP2001/2021 |

In case of early switch visit or premature interruption of treatment, the reference for changes computation within each period should be adjusted accordingly based on ESV visits.

First/Last Administration of Study Treatment

Considering the overall study, the date of first administration of treatment (i.e., velusetrag or placebo) is the earliest start date of the 4 periods reported in the “Study treatment dispensed” CRF page while the date of last administration of treatment (i.e., velusetrag or placebo) is the date reported in the “End of treatment disposition” CRF page (i.e., maximum of the last administration of the 4 periods).

According to the study design, subjects will not receive the treatment during the wash out periods. For each study period, the date of first administration of treatment is the start date reported in the “Study treatment dispensed” CRF page on the corresponding SOT visit (i.e., Visit 2 (SOT-1) for period 1, Visit 4 (SOT-2) for period 2, Visit 6 (SOT-3) for period 3 and Visit 8 (SOT-4) for period 4) while the date of last administration of treatment is the last treatment intake date reported in the “Study treatment returned” CRF page on the corresponding EOT visit (i.e., Visit 3 (EOT-1) for period 1, Visit 5 (EOT-2) for period 2, Visit 7 (EOT-3) for period 3 and Visit 9 (EOT-4) for period 4). In case of early switch visit or premature interruption of treatment, the first and last intake within each period should be adjusted accordingly.

Study day

The study day describes the day of the event or assessment date relative to the reference start date, which is defined as the date of Randomization.

The study day will be calculated as the difference between the date of each considered efficacy/safety assessment and the reference start date plus 1 day.

If the considered event starts before the Randomization date, the study day will be calculated as the difference between the date of the assessment and the reference start date. Therefore, the study day will be negative.

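### Does using V4, V6 and V8 as both one period's outcome and the next period's reference distort the treatment comparison for one secondary endpoint?

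*SAP*

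**What the plan says.** SAP 6.3.2 lists when this endpoint's levels are taken: before each treatment period, then "at the end of follow-up after the fourth period and at ETV and ESV". No end-of-treatment level is listed. Changes "will be computed between the end of each 2-week wash-out period (or follow up period) and the relevant pre-treatment values"; the visit pairs are written out, for example "for period 2: levels at V6 – levels at V4".

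The comparison method for this endpoint is redacted. Three readable places bear on it:

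- Protocol 16.3.2: "Continuous efficacy endpoints will be summarized and analyzed in the same way as the primary endpoint".
- SAP 6.3.1, for the primary endpoint: "Differences between velusetrag and placebo will be computed within each cycle". Under SAP 4.2, cycle 1 is periods 1 and 2, and cycle 2 is periods 3 and 4.
- SAP version history, draft 1.2: "Mixed models for efficacy parameters considered as continuous variables were updated considering the reference of" a model from a published comparison of N-of-1 methods. Its terms are not given.

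For early switchers, SAP 4.2 says "the reference for changes computation within each period should be adjusted accordingly based on ESV visits". Protocol section 6 allows the switch "without completing the ongoing treatment or washout period".

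**The concern.** In a crossover with separate outcome and reference visits, subtracting each period's own reference is routine. Here the reference for periods 2, 3 and 4 is the previous period's outcome. If velusetrag shifts the end-of-wash-out level, the shift counts once in the velusetrag period's change. It then sits in the next period's reference, so a placebo period that follows is charged with the return towards the starting level. A within-cycle difference would pick up both movements. The reported difference would then exceed the end-of-wash-out effect and would vary by sequence and cycle. An early switch could also place an on-treatment effect in a shared level.

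**Working it through.** **The plan's own figure.** The only design calculation concerns the primary endpoint: a paired t-test, two-sided 5%, 18 pairs, effect size 0.7, stated power 80%. The noncentral t gives 79.9%. No figure is stated for the endpoint in question.

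**Inputs.** Sequences A (VPVP), B (PVPV), C (VPPV) and D (PVVP), four subjects each, from SAP 3.1 and 3.3.2; cycles from SAP 4.2; changes from SAP 6.3.2. Two quantities are assumed, because the documents give neither:

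- d, the velusetrag-minus-placebo difference in end-of-wash-out level;
- c, the fraction of that effect still present at the next measurement, from 0 to 1.

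**Enumeration at c = 0.** Set the untreated level to 0. A level is d after velusetrag and 0 after placebo.

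| Sequence | Changes, periods 1 to 4 | Cycle 1, cycle 2 differences | Mean |
|---|---|---|---|
| A | d, −d, d, −d | 2d, 2d | 2.0d |
| B | 0, d, −d, d | d, 2d | 1.5d |
| C | d, −d, 0, d | 2d, d | 1.5d |
| D | 0, d, 0, −d | d, d | 1.0d |

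Balanced mean: (2.0 + 1.5 + 1.5 + 1.0)d / 4 = 1.5d.

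**General c.** The balanced mean is (1.5 − 0.5c)d, whether the effect carries over one period only (one-step) or decays geometrically. Least squares on the changes with subject, period and treatment terms returns the same values, so those terms alone do not remove the excess.

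**The alternatives.** Estimates in units of d, by least squares with 16 subjects and subject and period terms, except the direct contrast, which is (1 − 0.5c)d:

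| c | Stated changes | Changes + previous treatment: geometric / one-step | Levels + previous treatment: geometric / one-step | Direct contrast of levels |
|---|---|---|---|---|
| 0 | 1.50 | 1.00 / 1.00 | 1.00 / 1.00 | 1.00 |
| 0.25 | 1.375 | 1.05 / 1.07 | 0.98 / 1.00 | 0.875 |
| 0.5 | 1.25 | 1.07 / 1.14 | 0.93 / 1.00 | 0.75 |
| 0.75 | 1.125 | 1.05 / 1.21 | 0.84 / 1.00 | 0.625 |
| 1 | 1.00 | 1.00 / 1.29 | 0.71 / 1.00 | 0.50 |

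No column is closest to 1 in every row.

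**Precision.** With independent errors, the treatment estimate from levels has variance 0.0982 error variances with a previous-treatment term and 0.0625 without: 0.0982 / 0.0625 = 1.57. By least squares the ratio rises to about 2.0 and 2.3 at visit correlations of 0.5 and 0.9.

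Power below is for 32 pairs and effect size 0.7 (borrowed from the primary endpoint), at visit correlations 0, 0.5 and 0.9:

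- Levels with previous treatment: 87%, 82%, 84%.
- Stated changes at c = 0: 91%, 95%, 98%.
- Stated changes at c = 1: 60%, 68%, 75%.

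The level model loses power where the stated changes are most inflated, and gains it where they are unbiased.

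**Early switch.** Let E be an on-treatment effect captured at the early switch visit, with nothing left after a full wash-out. A switch during a velusetrag period adds 2E to that subject's two cycle differences in five of the six possible slots, and 0 in sequence D, period 2. A direct comparison of levels would already carry E. The overlap itself therefore adds at most 2E − E = E, or E/32 ≈ 0.031E in a mean of 32 pairs, and in the sixth slot it removes contamination.

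**The case for a change.** The case for a change is not weak. The visit overlap is explicit, the arithmetic is exact, and the usual crossover terms do not cure it. Protocol 16.3.2 points towards the within-cycle contrast that produces the inflation. A wash-out length chosen from half-life (protocol section 7) does not settle how long an effect on these levels lasts. Good wash-out between measurements (c near 0) gives the largest proportional distortion of whatever effect remains. The 50% is also not a ceiling: at c = 0, sequence counts of 6/3/4/3 give (6×2 + 3×1.5 + 4×1.5 + 3×1)/16 = 1.59, and a rebound with c = −0.25 gives 1.625. Stating how the reference enters the model would cost one sentence.

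What stands is the conditional result: if the comparison is a plain contrast of these changes, and if the end-of-wash-out level is the target, the contrast is inflated. Neither condition can be established. The version history says continuous efficacy parameters moved to a different mixed model, and redacted text cannot be read as an omission. The quantity the SAP defines is the change over the period; d is the reader's construct.

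**Conclusion.** No change to the plan follows. The shared visits are real, and under a plain contrast of changes with balanced sequences they would give (1.5 − 0.5c)d: an overstatement of 0 to 50% for c between 1 and 0. That rests on an assumed c, an assumed target and an unread model. With d = 0 the expected contrast is 0, so the overlap can alter the size of an effect but not create one. The primary endpoint takes outcome and reference at different visits and does not share this overlap.

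The choice among analyses is a fair trade-off. A previous-treatment term removes the inflation at c = 0. At c = 1 it can move the estimate further from d than the stated changes do: 0.71d for levels under geometric decay, 1.29d for changes under one-step carry-over. It also costs precision. Which is better turns on a persistence that the documents do not give and on whether the period change or the end-of-wash-out level is of interest, so statisticians could reasonably differ. How the reference and the early-switch levels enter the model is a detail the redacted method may already cover, and analysts can settle it when they apply the adjustment in SAP 4.2.
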